There is evidence that sciatic PNB, regardless of technique, significantly reduces pain when compared to intravenous opioids during the initial 24-hour postoperative period following knee surgery (Wegener, van Ooij, van Dijk, Hollmann, Preckel, & Stevens, 2011). As such, single-injection sciatic PNB, which can last up to 24 hours, should provide adequate analgesia precluding the need for oral narcotic or nonsteroidal anti-inflammatory medications following ACL reconstruction with a hamstring autograft. It remains unknown, however, if any benefit is gained during the initial 72-hour postoperative period from extending analgesia for the hamstring donor site via continuous sciatic PNB. While continuous sciatic PNB with a CPI catheter extends the duration of analgesia, it also extends the duration of anesthesia potentially leading to a decrease in motor function and subsequently active knee flexion. The sciatic nerve innervates the hamstrings, which are responsible for knee flexion (Distad &

Weiss, 2013). The decrease in active knee flexion may impede the ability of the patient to begin rehabilitation on the first postoperative day. This is an important consideration because early rehabilitation, which includes contraction of the quadriceps and hamstring muscles as well as weight bearing exercises with the aid of crutches, leads to faster recovery of long-term range of motion and a lower incidence of knee laxity following ACL reconstruction when compared to delayed rehabilitation (Shaw, Williams, & Chipchase, 2005; Pinczewski et al., 2007). Determining the duration of sciatic PNB required to effectively control pain following ACL reconstruction with a hamstring autograft, without impeding active knee movement, will help define best practice going forward.

II. RESEARCH QUESTION

This study aims to answer the following research question: Does the duration of sciatic PNB impact the ability to effectively provide postoperative pain control following ACL reconstruction with a hamstring autograft in the adolescent population?

III. PURPOSE OF THE STUDY

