The purpose of this research is to compare the effect of single-injection sciatic PNB to continuous sciatic PNB on 1) postoperative pain control as measured by self-reported pain scores, pain medication use, and unplanned hospital admission due to poor pain control, 2) active knee flexion, and 3) patient satisfaction with pain control following ACL reconstruction with a hamstring autograft. The results of this research have the potential to positively impact pain control for the adolescent population undergoing this surgical procedure and foster responsible utilization of limited resources.

SPECIFIC AIM 1. The first aim of the study is to explore the impact of sciatic PNB technique on hamstring donor site pain control postoperatively.

H1.a. The extended duration of analgesia offered by continuous sciatic PNB decreases pain scores during the initial 72 hours following hamstring autograft harvest when compared to single-injection sciatic PNB.

H1.b. The extended duration of analgesia offered by continuous sciatic PNB decreases oral pain medication use during the initial 72 hours following hamstring autograft harvest when compared to single-injection sciatic PNB.

H1.c. The extended duration of analgesia offered by continuous sciatic PNB decreases the incidence of unplanned admission due to poor pain control during the initial 72 hours following hamstring autograft harvest when compared to single-injection sciatic PNB.

SPECIFIC AIM 2. The second aim of the study is to explore the impact of sciatic PNB technique on active knee flexion postoperatively.

H2. The extended duration of analgesia offered by continuous sciatic PNB does not delay active knee flexion during the initial 72 hours following hamstring autograft harvest when compared to single-injection sciatic PNB.

SPECIFIC AIM 3. The third aim of the study is to explore the impact of sciatic PNB technique on patient satisfaction with postoperative pain control.

H3.1. The extended duration of analgesia offered by continuous sciatic PNB improves patient satisfaction during the initial 72 hours following hamstring autograft harvest when compared to single-injection sciatic PNB.

IV. PREVIOUS CLINICAL EXPERIENCE

Concurrent Research Studies: The Department of Anesthesiology is not currently conducting another protocol with this patient population.

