The hypothesis that the extended duration of analgesia offered by continuous sciatic PNB decreases pain scores during the initial 72 hours following hamstring autograft harvest when compared to single-injection sciatic PNB will be tested with two separate tests. Both Pearson's correlation and the Wilcoxon Mann Whitney test will be utilized to test his hypothesis, as controversy surrounds the analysis of Likert scale data. It has been argued that only nonparametric statistics should be used on Likert scale data, as the intervals between the scale values may not be equal (Jamison, 2004). Taking this into consideration, the pain scores recorded for each patient will be totaled and an average pain score will be calculated for each study participant. This will allow the data to be measured on a continuous scale, thereby meeting the criteria of Pearson's correlation. Pearson's correlation is a parametric test that measures the degree and direction of linear relationship between two variables (Gravetter & Wallnau, 2000). The Wilcoxon Mann Whitney test will also be used to analyze pain scores recorded at each 12-hour period to determine if there is a difference in outcomes related to the duration of analgesia provided by sciatic PNB technique. This test is appropriate when there is one IV with two independent groups and the DV is ordinal in nature. The Wilcoxon Mann Whitney test is a nonparametric test of the null hypothesis that two populations are the same against an alternative hypothesis. This test uses the relative position of the data in a rank ordering, rather than the actual values. Using both parametric and nonparametric tests will increase confidence when drawing conclusions should both tests lead to the same results.

The hypothesis that the extended duration of analgesia offered by continuous sciatic PNB decreases oral pain medication use during the initial 72 hours following hamstring autograft harvest when compared to single-injection sciatic PNB will be tested with the Independent Samples *t*-Test. The Independent Samples *t*-Test is appropriate when there is one IV with two independent groups and the DV is continuous in nature (Field, 2009). The Independent Samples *t*-Test is used to compare differences between separate groups when there are two experimental groups (single-injection sciatic PNB and continuous sciatic PNB) and different study participants have been used in each group (Field, 2009).

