The hypothesis that the extended duration of analgesia offered by continuous sciatic PNB decreases the incidence of unplanned admission due to poor pain control during the initial 72 hours following hamstring autograft harvest when compared to single-injection sciatic PNB will be tested with the Chi-square test. The Chi-square test is used to determine if there is a relationship between two categorical variables (Field, 2009). As the data for this DV are categorical, the focus during analysis is placed on frequencies rather than means. The Chi-square test can be used to determine if there is a significant difference between the expected frequencies and observed frequencies in one or more categories (Field, 2009).

The hypothesis that the extended duration of analgesia offered by continuous sciatic PNB does not delay active knee flexion during the initial 72 hours following hamstring autograft harvest when compared to single-injection sciatic PNB will be tested using the Wilcoxon Mann Whitney test. The hypothesis that the extended duration of analgesia offered by continuous sciatic PNB improves patient satisfaction during the initial 72 hours following hamstring autograft harvest when compared to single-injection sciatic PNB will also be tested using the Wilcoxon Mann Whitney test. The Wilcoxon Mann Whitney test is appropriate to test both these hypotheses, as this test is designed to evaluate the difference between two treatments (single-injection sciatic PNB and continuous sciatic PNB) using data from an independent measures study (Gravetter & Wallnau, 2000). During analyses, testing may be altered based on the recommendations of the statistician to better analyze the collected data. Intention-to-treat analysis will not be employed, as this may skew results and it is often difficult to obtain outcome data for study participants who have dropped out of the study (Polit & Beck, 2012).

Prior to any analyses, the distribution of the demographic variables will be compared between the two treatment groups. All statistical tests will be two-sided with a significance level of $\alpha=0.05$ and will be conducted using SAS[®] software, (Version 9.2, Cary, NC). Following the enrollment of the initial 30 subjects (with 15 in each study group), an interim analysis utilizing the statistical tests later described will be performed to determine if statistically

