Appendix B

Post-Discharge Data Collection Instrument

PAIN CONTROL:

Keep track of your pain score and location of pain:

Pain score: 0 = no pain, 10 = worst pain			
Pain location: F = front of knee, B = back of knee, X = both front & back			
6 hours		42 hours	
12 hours		48 hours	
18 hours		54 hours	
24 hours		60 hours	
30 hours		66 hours	
36 hours		72 hours	

Date and time the leg was no longer numb behind the knee: _____

Pain medicine prescribed (circle one): Vicodin Percocet Other: _____

Write down every time pain medication is taken:

[illegible]

ACTIVE KNEE MOVEMENT:

Rate the ability to bend the knee that was operated on:

Knee Movement	12 hours	24 hours	36 hours	48 hours	60 hours	72 hours
0 = Able to bend with no pain						
1 = Able to bend, but with pain						
2 = Too much pain to bend						

SATISFACTION:

Rate your overall satisfaction score with pain management:

Satisfaction Score	12 hours	24 hours	36 hours	48 hours	60 hours	72 hours
0 = Not satisfied at all						
1 = Not satisfied						
2 = Partially satisfied						
3 = Satisfied						
4 = Highly satisfied						

From your perspective, have you encountered any unexpected postoperative experiences?

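### H2 (continuous block does not delay knee flexion) cannot be supported by a two-sided difference test with no margin, and the diary scale has no level for a knee that motor block stops from bending

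*Combined protocol and SAP*

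**What the plan says.** **Hypothesis.** H2 in Section III is a claim of no harm: continuous sciatic block "does not delay active knee flexion during the initial 72 hours following hamstring autograft harvest when compared to single-injection sciatic PNB".

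**Test.** Section VI.B assigns it a difference test, the Wilcoxon Mann Whitney. The wording there is: "does not delay active knee flexion during the initial 72 hours following hamstring autograft harvest when compared to single-injection sciatic PNB will be tested". The same section describes that test as a "nonparametric test of the null hypothesis that two populations are the same against an alternative hypothesis", and justifies it for H2 and H3 because "this test is designed to evaluate the difference between two treatments". All tests are two-sided at 0.05. No margin, confidence-interval rule or sample size is given for H2. The 64 per group in Section V.D rests on pain scores.

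**Mechanism of concern.** Section I says of the continuous technique that "it also extends the duration of anesthesia potentially leading to a decrease in motor function and subsequently active knee flexion".

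**Measurement.** The Appendix B knee item is completed every 12 hours to 72 hours. It runs from "0 = Able to bend with no pain", through able to bend but with pain, to "2 = Too much pain to bend". Section V.G describes the item as pain associated with flexion. The time at which numbness behind the knee ended is also recorded, but it is sensory and has no planned analysis.

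**The concern.** There are two separate problems.

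First, H2 sits on the null side of its own test. Failing to reject equality shows only that the data did not separate the arms. Without a margin, nothing in the plan says how large a delay must be ruled out before the claim can be made.

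Second, the scale grades pain, while the stated harm is loss of motor function. A patient without pain whose hamstrings are blocked cannot truthfully tick 0 or 1 (both say able to bend) or 2 (which blames pain).

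Flexion is one of three specific aims, and Section I ties early movement to rehabilitation and long-term range of motion. The trial could therefore appear reassuring about a recognised argument against the continuous technique without having the evidence.

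**Working it through.** **1. The plan's own figure.** For a standardized effect of 0.5, two-sided alpha 0.05 and power 0.80, the normal approximation gives 63 per arm and the t-test 63.8, rounded up to 64. Section V.D's 64 reproduces, but it is a figure for a pain-score difference.

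**2. What a non-significant result would mean.** The documents give no flexion rates, so those below are assumptions. Take 64 per arm, 80% able to bend on single injection, one assessment and a two-proportion test:

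power = Φ[(d − 1.96·√(2p̄(1−p̄)/n)) / √((p₁(1−p₁)+p₂(1−p₂))/n)], where d = p₁ − p₂ and p̄ is their mean.

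For 80% v 70%: (0.10 − 1.96×0.0765)/0.0760 = −0.658, so power is 0.255.

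| Able to bend, single v continuous | Power | Chance of non-significance |
|---|---|---|
| 80% v 70% | 0.255 | 74.5% |
| 80% v 65% | 0.476 | 52.4% |
| 80% v 60% | 0.699 | 30.1% |

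The planned test is a rank test on three levels, so I also simulated that (64 per arm, one assessment, 3,000 runs). With assumed levels 0/1/2 of 30/50/20% on single injection, a shift to 25/47.5/27.5% was non-significant in 84% of runs (1 − 0.160). A shift to 22/45/33% was non-significant in 62% (1 − 0.376).

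**3. What the scale does to motor block.** Same simulation, with an assumed share of the continuous arm painless but unable to bend. Entries are the percentage of runs significant, with the direction.

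| Pain in the rest of the continuous arm | Share blocked | Tick 2 | Blank | Tick 0 |
|---|---|---|---|---|
| Same, 30/50/20% | 20% | 39.7, against continuous | 4.6, chance level | 31.9, for continuous |
| Same, 30/50/20% | 30% | 70.2, against | 4.1, chance level | 61.8, for |
| Lower, 45/45/10% | 20% | 5.3, mixed | 48.2, for | 89.8, for |
| Lower, 45/45/10% | 30% | 19.8, almost all against | 44.4, for | 96.6, for |

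The same physical state can give opposite conclusions according to how patients cope with a form that does not fit them.

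**4. Precision available.** The 95% CI half-width for a difference in proportions at one time is 1.96·√(2p(1−p)/64):

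- p = 0.9: 1.96×√(0.18/64) = 0.104
- p = 0.8: 1.96×√(0.32/64) = 0.139
- p = 0.5: 1.96×√(0.50/64) = 0.173

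**5. Size for a non-inferiority claim.** With no true difference, one-sided 0.025 and 80% power, n per arm = (1.96+0.842)²·2p(1−p)/margin². At p = 0.8, margins of 10, 15 and 20 points need 252, 112 and 63 per arm. At p = 0.9 they need 142, 63 and 36.

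**6. When the arms differ in exposure.** Section I says a single injection can last up to 24 hours. Section V.A runs the catheter for 48 hours. At 24 hours both arms may be blocked, or the single-injection arm only just recovered. The clearest contrast is after that, up to about the 48-hour entry. H2 itself speaks of delay over 72 hours, yet Section VI.B gives no rule for combining the six assessments.

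**The case against.** A reader might infer that H2 cannot be answered at all. The documents do not support that: a significant result against continuous block would contradict H2. What is missing is any result that could establish it.

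A reader might also infer that the scale must bias the trial towards reassurance. That is not certain. The form asks for ability to bend, and level 2 is the only cannot-bend answer, so some blocked patients may tick it and the inability would be recorded. Reassurance is a likely direction, not a demonstrated one.

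Other points on the plan's side have some weight. Aim 2 is worded as exploratory. No sentence says that a non-significant H2 result will be reported as proof; the text in Section VI.B that pairs equivalence with non-significance concerns continuing after the interim analysis. Motor block is not wholly invisible, because falls are monitored, untoward events are collected daily and the diary ends with an open question. None of these measures flexion.

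Two provisions might seem to cure the problem. The five-volunteer pilot in Section V.G allows the form to be revised, but nothing commits to adding this level. Section VI.B lets the statistician alter tests, but that supplies no margin before the data are seen and cannot recover motor block that was never recorded.

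**Conclusion.** The concern holds in this form: the planned analysis can contradict H2 but cannot support it, and the flexion scale leaves the recording of motor block to chance. Both follow from the text and need no assumed figures.

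The sizes do rest on assumptions. The 80% baseline, the level distributions and the 20% to 30% motor-block shares are not in the documents. The two-proportion powers describe one time point, not the planned rank test; the rank-test simulation points the same way, but also for a single assessment. Under these assumptions, 64 per arm would often miss a 10- to 15-point deficit. It would give about 80% power for no delay only with a wide margin, about 20 points at 80% able to bend or 15 points at 90%.

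**What to change.** - **Scale, before the pilot.** Make the Appendix B item record inability to bend from any cause, for example by adding '3 = Cannot bend because the leg is too weak or numb', and count levels 2 and 3 as unable to bend.
- **Endpoint.** Define it over assessments that include the period when only the continuous arm is still being infused (36 and 48 hours as well as 24), or as time to first able to bend within 72 hours. Do not use 24 hours alone: a diluted contrast would favour declaring no delay.
- **Decision rule.** Claim no delay only if the two-sided 95% CI for the between-arm difference excludes a margin that the sponsor justifies before enrollment. Otherwise restate H2 as a difference reported with its CI, and make no claim of no delay.
- **Precision.** State the expected half-widths at 64 per arm: about 10, 14 or 17 points at an assumed 90%, 80% or 50% able to bend.

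The cost is one diary line and a rewritten H2 paragraph. The downside is that the no-delay claim becomes harder to make, and a narrow margin would be out of reach at the planned size.

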Power analysis was performed to estimate an adequate sample size to support statistical conclusion validity and so that correct inferences can be made about the relationships between study variables. The standardized effect size was calculated to equal 0.5. Assuming an alpha of 0.05, power of 0.80 and a standardized effect size of 0.5, 64 patients will be required for each treatment group based on anticipated difference in patient reported pain scores due to sciatic PNB technique. Projected sample sizes were increased approximately ten percent from 64 per group to total of 70 subjects per group in an effort to account for patient attrition and lost data, therefore, a total of 140 patients will be enrolled in the study. Additionally, if the loss in patients is unequal between groups, yielding a significant disparity between study group composition, additional subjects may be added to account for this unequal loss.

Despite the presence of multiple confounding variables, the calculated sample size is sufficient to determine if a significant difference in outcomes measures exists secondary to sciatic PNB technique. Additionally, the sample size does not need to be altered based on the equation: $N > 50 + 8k$, where N is the number of cases and k is the number of predictors (Warner, 2013). In this study there is only one predictor, sciatic PNB technique, which is anticipated to impact outcomes following ACL reconstruction.

E. Randomization:

A computer generated randomization scheme will be used to assign 70 patients to each treatment group. The randomization will be done using the maximum allowable percent deviation method. This algorithm conducts a search to find a randomization list for which all percent deviations are less than or equal to the maximum allowable percent deviation of 10%. The randomization scheme will be sent to the PI who will then prepare and maintain a log of subject assignments. The PI will notify the participating surgeon and anesthesia team of the treatment (single-injection or continuous sciatic PNB) that is to be given to the next consented patient. The research coordinator will remain blinded to the assigned treatment plan until data collection has been completed.

F. Components of Cincinnati Children's Hospital Medical Center to be Utilized for this Study:

Subjects undergoing unilateral ACL reconstruction with a hamstring autograft on an outpatient basis at the Liberty Campus of CCHMC will be recruited from the OR schedule.

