date and time their leg was no longer numb behind their knee. The orthopedic surgeon performing the ACL reconstruction or a member of his orthopedic team will prescribe all postoperative oral pain medication. The oral pain medication typically prescribed is either Percocet or Vicodin. Vicodin, a schedule 3 controlled substance, is approximately half as potent as Percocet, which is a schedule 2 controlled substance. The patient will record the time and dose of all oral pain medication taken during the 72 hours postoperative period. The patient or their guardian will also record data regarding pain associated with active knee flexion once every 12 hours for 72 hours postoperatively. In addition, the patient or their guardian will record satisfaction with pain control once every 12 hours for 72 hours postoperatively.

The research coordinator may collect all data recorded by the patient and/or their guardian via telephone interview. Data will be collected using the same data collection tool given to the study participants to avoid instrumentation and maintain interrater reliability. Untoward events, such as unplanned hospital admission, CPI catheter dislodgement, or local anesthetic toxicity, will also be noted should they occur. This information will be collected from the patient or guardian once every 24 hours by the research coordinator during the 72-hour postoperative period; the postoperative period begins at the time of discharge from the PACU.

1. Survey(s) and Questionnaire(s):

Patients and their guardian will be given data collection instruments to complete postoperatively at the time of enrollment to facilitate recall when conveying information to the study staff during telephone conversations. The data collection instruments will be available in different languages and utilized for non-English speaking patients and/or guardians. The patient and their guardian(s) will receive training regarding the data collection tool both during the time of enrollment and again prior to discharge from the hospital. At the time of enrollment, essential phone numbers, including home phone and cell phone numbers, will be collected. Should the patient and/or guardian lose the data collection sheet, additional copies can be emailed to them upon request. Hospital-approved interpreters will be utilized for non-English speaking patients and/or guardian(s).

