Each enrollment will take variable time to complete depending on the length of the surgical procedure and amount of time required in the recovery room. Following enrollment, data is collected for 72 hours postoperatively. The entire study will take approximately 2 years to enroll and complete.

VI. DATA STORAGE AND STATISTICAL ANALYSIS

A. Data Storage:

Data confidentiality will be maintained by data being stored in a password protected computer and hard copies of subject information stored in a locked office. All data is collected from the study participant will be entered into REDCap™ (Park City, Utah) by the research coordinator. REDCap™ is a secure web application for building and managing databases securely that was specifically designed to support clinical and translational research

(Harris, Taylor, Thielke, Payne, Gonzalez, & Conde, 2009). Confidentiality of the data will be maintained through the use of a password-protected computer and any hard copies of subject information stored in a locked office accessible only to members of the Department of Anesthesia.

The study records will be made available for review only to the Institutional Review Board and the Food and Drug Administration (FDA) per CCHMC policy. The FDA is a branch of the federal government that establishes regulations and guidelines for clinical research to protect participants from unreasonable risks. Furthermore, the FDA ensures consumers have reliable information and that medical treatments are not only safe, but effective as well. The subjects' names or any other identifiers will not be used in published information relating to this study and will be treated as confidential per the Health Insurance Portability and Accountability ACT (HIPAA) of 1996. Per the HIPAA Privacy Rule, prior to dissemination of results, all health information will be deemed individually unidentifiable by employing the approved Safe Harbor method of de-identification that entails the removal of 18 types of identifiers.

B. Primary Endpoint Analysis:

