significant differences exist between the outcome measures of each sciatic PNB technique. Performing an interim analysis limits the number of patients exposed to study procedures. If statistically significant differences exist such that one of the two sciatic PNB techniques clearly produces superior patient outcomes, the study will be stopped. However, should the outcomes measures of each sciatic PNB technique be found to be equivalent and without statistically significant differences enrollment will continue.

VII. DATA SAFETY AND MONITORING

Adverse events will be collected until data collection is complete. Adverse events will be recorded on the case report forms. Details will include an explanation of the event, seriousness, anticipation, treatment, resolution and relatedness to the study treatment. All study-related adverse events will be followed through to completion

A. Adverse Event Definitions:

The definitions for adverse event, adverse device effect, serious adverse event, serious adverse device effect, and unanticipated adverse device effect are provided below (ANSI/AAMI/ISO 14155-2:2003, 21 CFR 812.3(s)).

Adverse Event: an adverse event is any untoward medical occurrence in a subject, which need not be related to the treatment under investigation.

Adverse Peripheral Nerve Blockade Blockade Effect: an adverse peripheral nerve blockade effect is any untoward or unintended response to regional blockade, which may result from insufficiencies in the deployment of the ultrasound machine, or from provider error.

Serious Adverse Event: a serious adverse event is an adverse event that results in death, inpatient hospitalization, severe or permanent disability, a life threatening illness or injury, fetal distress, fetal death, a congenital abnormality, a birth defect, or medical or surgical intervention to prevent permanent impairment to body or structure.

Serious Adverse Peripheral Nerve Blockade Effect: a serious adverse peripheral nerve blockade effect is an adverse regional blockade effect that results in death, inpatient hospitalization, and severe or permanent disability or is life threatening.

Unanticipated Peripheral Nerve Blockade Effect: any serious adverse effect on health or safety or any life threatening problem or death caused by, or associated with, peripheral nerve blockade if the effect, problem, or death was not previously identified in nature, severity or degree of incidence in the

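### Five hypotheses are tested at unadjusted 0.05 as primary, with no single primary endpoint or test named, although the trial is sized on pain scores alone

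*Combined protocol and SAP*

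**What the plan says.** - **Heading and scope.** All hypothesis tests in section VI stand under "B. Primary Endpoint Analysis". They cover H1.a (pain scores), H1.b (oral pain medication), H1.c (unplanned admission), H2 (active knee flexion) and H3.1 (satisfaction). There is no secondary-endpoint section, no ranking and no adjustment.
- **Level.** "All statistical tests will be two-sided with a significance level of" 0.05.
- **Sizing.** Section V.D: "Assuming an alpha of 0.05, power of 0.80 and a standardized effect size of 0.5, 64 patients will be required for each treatment group", and this is "based on anticipated difference in patient reported pain scores". No other outcome enters the calculation.
- **Pain tests.** Section VI.B plans Pearson's correlation on each patient's average pain score and also a Wilcoxon test at each 12-hour period. It says that agreement between the two would raise confidence, but gives no rule for disagreement.
- **Flexion and satisfaction.** Each is rated six times. For satisfaction, section V.G has the patient or guardian "record satisfaction with pain control once every 12 hours for 72 hours postoperatively"; flexion follows the same schedule. Section VI.B assigns each a Wilcoxon test without naming a time point or a summary.
- **Interim look.** After 30 patients (15 per group) the tests are applied to the outcome measures. "If statistically significant differences exist such that one of the two sciatic PNB techniques clearly produces superior patient outcomes, the study will be stopped". No interim significance level is given.
- **Latitude.** Section VI.B also lets the tests be changed during analysis on the statistician's advice.

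**The concern.** The plan treats one outcome as primary when it sets the sample size and five as primary when it draws inferences. Nothing written in advance says which result decides whether the trial is positive. Any of the five, or any of several pain tests, could be presented as a primary result at the nominal 5% level. The overall chance of a false claim is then well above 5%, and a reader of the final report could not tell which test was meant to carry the conclusion.

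The interim look adds to this. It applies the same unadjusted tests to every outcome when 30 of 140 patients are enrolled, and a favourable result can end the trial.

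**Working it through.** **1. The plan's own figure.** Inputs from section V.D: standardized effect 0.5, alpha 0.05, power 0.80. A two-sided two-sample t-test needs 63.8, so 64 per group, with power 0.801 at 64. The stated 64 is reproduced, and it assumes one test of pain at the full two-sided 0.05.

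**2. Tests actually written.** Pearson on the pain mean (1), Wilcoxon on pain at each 12-hour period (72/12 = 6), medication t-test (1), admission chi-square (1), flexion Wilcoxon (1), satisfaction Wilcoxon (1). Total: 11.

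**3. One test per hypothesis, final analysis only.** The chance of at least one p<0.05 with no true differences, if independent, is 1 - 0.95^k.
- Five hypotheses: 1 - 0.95^5 = 22.6%.
- Four superiority hypotheses, without H2: 1 - 0.95^4 = 18.5%.
- Five hypotheses, test statistics simulated as equally correlated normal variables: 20.8% at correlation 0.3, 18% at 0.5, 10.2% at 0.9.

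**4. The 11 written tests.** Simulated with an assumed correlation of 0.5-0.7 within pain and 0.1-0.5 between outcomes. The result depends somewhat on how the test on the pain mean is related to the six 12-hour tests:

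| Treatment of the pain-mean test | Within 0.5, between 0.1 | Within 0.7, between 0.5 |
|---|---|---|
| Seventh equally correlated pain test | 37% | 27% |
| Exact mean of the six 12-hour scores | 35% | 25% |

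The planned mean uses all 12 six-hourly scores, so neither model is exact. About 27-37% under the first and 25-35% under the second is a fair statement.

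**5. Adding the unadjusted interim look.** Information fraction 30/140 = 0.214, so the interim and final statistics correlate at sqrt(0.214) = 0.463.
- One test at both looks, each at 0.05: 9.2%.
- Five independent tests at both looks: 1 - (1 - 0.092)^5 = 38%.
- Five tests with correlation 0.5: about 31%.

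**The case against.** Several points on the other side are fair.

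- **The aims are worded as exploration.** For example: "The third aim of the study is to explore the impact of sciatic PNB technique on patient satisfaction". The same section nevertheless states formal hypotheses, and section VI.B tests each for significance under the primary heading and lets the outcomes inform stopping. The wording of the aims does not remove the problem.
- **Flexion and satisfaction are not stated to be tested six times.** A reader might count six Wilcoxon tests for each and reach 21 tests in all. Per-period testing is written only for pain; being rated six times is not the same as being tested six times. A reader might also infer that the six ratings would be pooled as if independent. The documents never propose that, and a per-patient summary, which the plan already uses for pain, is an equally open route. What stands is that the time point or summary is unspecified.
- **H2 predicts no delay.** A false-positive difference showing delay would contradict H2, not confirm it. Counting only errors in the hypothesised direction for the four superiority hypotheses gives 1 - 0.975^4 = 9.6% if independent. That is still about twice 5%, and against a one-direction standard of 2.5% it is nearly four times.
- **Admissions may be rare.** The chi-square test then contributes less than 5%. With 70 per group it rejects about 0.5% of the time at an assumed admission rate of 1%, and about 2.6% at 2%. The documents give no rate.
- **The stopping rule is not purely mechanical.** It asks that one technique be clearly superior. A reader might infer that any single p<0.05 stops the trial, but the text does not say so. It does leave undefined which outcomes count and how strong the evidence must be, so the two-look figures describe declaring significance at either look and are not a predicted stopping rate.

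**Conclusion.** The point holds. Five hypotheses share the primary heading at unadjusted 0.05, no single primary endpoint or test is named, and the sample size supports only one of them. With no true differences, the chance of at least one nominally significant result is:

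- 22.6% for five independent tests, and about 10-21% for assumed equal correlations of 0.9 down to 0.3;
- 18.5% for the four superiority hypotheses if independent, less if admissions are rare;
- roughly 25-37% for the 11 or so tests written;
- about 31-38% for five tests plus the unadjusted interim look, at assumed correlation 0.5 down to 0.

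All correlations are assumptions. It would be tempting to say that a false-positive primary result is likely. The documents do not support that: on the tests as written the chance is several times the nominal level but below one half. The sample-size figure itself is not in error.

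**What to change.** 1. Name H1.a as the sole primary endpoint, with one pre-specified test on one per-patient pain summary (for example the 72-hour mean already planned), at an overall two-sided 0.05. Make the 12-hour pain tests supportive. This also settles which of the two pain methods decides.
2. Move H1.b, H1.c, H2 and H3.1 under a secondary heading, reported with estimates and 95% intervals and not as confirmatory.
3. State one per-patient summary of the six ratings for each of H2 and H3.1, each in a single Wilcoxon test. For H2 choose a summary that reflects delay, which a plain average of the 0-2 ratings in Appendix B would not do well.
4. Limit the interim efficacy rule to the primary endpoint and give it an alpha-spending boundary, for example O'Brien-Fleming type. Limiting the endpoint alone is not enough, because one test with an unadjusted look still has about 9.2% error. At 30/140 such a boundary spends 4 × [1 - Φ(2.241/0.463)], about 0.000003, so it requires |z| of about 4.7. The final test stays essentially at 0.05.

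**Cost.** Wording only; 64 per group remains adequate. A significant secondary result can no longer be claimed as a primary finding, and stopping for efficacy at 30 patients becomes very improbable. The alternative of keeping all five as primary with Bonferroni (0.01 each) would need about 94-96 per group, or would leave power of about 0.59 with 64 per group.
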